3.1 Primary Objective

To significantly improve tinnitus loudness as measured by VAS, when using intranasal oxytocin compared to placebo.

4 Study Design and Endpoints

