Brief Summary	The purpose of this study is to evaluate the effects of high-dose intranasal oxytocin for treating tinnitus. The hypothesis is that high dose intranasal oxytocin can significantly reduce tinnitus severity and disability.
Methodology	Pilot, proof of concept, randomized, placebo-control, parallel study
Endpoint	The primary efficacy endpoint is the area under the VAS curve from baseline for all randomized participants during the blinded study phase. The secondary endpoint, which is exploratory, will be improvement ($p < 0.10$) in the Tinnitus Handicap Inventory Severity Scale (THI)/Clinical Global Impression Scale (CGI) and Tinnitus Functional Index (TFI).
Study Duration	Time from when the study opens to enrollment until completion of data analysis will be approximately 1 year.
Participant Duration	Participant participation will last approximately 4 months and involve about 17 visits.
Duration of IP administration	Investigational product administration will last 15 weeks. The first 9 weeks of this period will involve the administration of active study medication to all participants. During the last 6 weeks, participants will be randomized to receive either placebo or active study medication for the remainder of the study.
Population	We will recruit patients from NYU Langone Medical Center's Departments of Otolaryngology and Neurology. Eligible individuals will be age 18 to 75 with continuous perception of tinnitus for > 6 months, with a normal ENT evaluation within the past year.
Study Sites	NYU Langone Medical Center
Number of participants	50 participants expected to be enrolled with a goal of 30 study participants remaining after accounting for screen failures and participants who withdrew from the study.
Description of Study Agent/Procedure	The investigational product, oxytocin nasal spray (45 units/0.1mL for 100mL) is composed of: oxytocin 10 unit/MG/mannitol trituration (4.500g), magnesium chloride crystals (6.080g), citric acid anhydrous gran. (0.284g), sodium citrate powder (5.660g), sterile water for irrigation (100.000mL), and Pcca Mucolox liquid base (10.000mL). The dose for the oxytocin nasal spray will range from 30 to 45 IU per puff to be administered four times per day, for an equivalent to 120 to 180 IU oxytocin/day.

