7.2.3 Intermediate Visits

7.2.3.1 Visit 3: End of Week 1 (Office Visit)

- Record adverse events as reported by participant or observed by investigator.
- Record vital signs and auscultate lungs.
- Review current medications and results of VAS log.
- Perform urine pregnancy test, if applicable.
- Administer THI questionnaire.
- Provide the study medication to the participant to use four times daily for the next 2 weeks.

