7.2.3.9 Visit 11: Week 9 (Office Visit)

- Record vital signs and auscultate lungs.
- Review current medications and results of VAS log.
- Collect urine for electrolyte levels and urine osmolality. Perform urine pregnancy test, if applicable.
- Administer THI and CGI-I questionnaires.
- Record adverse events as reported by participant or observed by investigator.
- Study drug reconciliation and record of participant's adherence to treatment program.
- Randomize and dispense new study drug (active drug or placebo nasal spray) to use for the next 2 weeks.

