9.2 Statistical Hypotheses

We hypothesize that treatment with high dose oxytocin nasal spray will result in a large effect size as measured by partial eta squared for the difference in mean area under the curve in baseline adjusted VAS when compared to placebo during the blinded study phase.

The primary outcome measurement will be the collective area under the VAS curve above the week 3 baseline as assessed from week 3 to week 6 of the blinded study phase. The area under the curve will be determined using the linear trapezoidal method for each participant after subtracting the baseline (week 3) VAS value from each subsequent measure to determine the collective improvement/decline of the VAS measurement during the blinded study phase. The mean and standard deviation of the total area will be

calculated for each study arm (active drug and placebo) and partial eta squared effect size for the difference determined. This effect size estimate can then be used to power future comparative studies.

The same area under the curve above the baseline VAS metric will be determined separately for the nonblinded/open label study phase. The inherent bias of non-blinding may influence this metric although the relatively larger sample size (n=30) could also improve precision. Therefore, the area will be presented as a descriptive summary using the mean and standard deviation with an effect size estimate.

Secondary endpoints will consist of safety and tolerability metrics including adverse event incidence and severity, regimen adherence and voluntary study drop-out rates reported during the non-blinded and blinded study phases. The frequency and percentage of each secondary measure will be determined for the non-blinded study phase and by study arm for blinded study phase. Additionally, any changes in THI greater than 1 grade will be determined from week 3 to week 6 of the blinded study phase. The frequency and percentage of these changes will be summarized by study arm.

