9.5 Sample Size

This is a pilot, proof of concept study with the main goal of providing an estimate of the effect size difference between treatment and placebo control. As such the sample size of n=30 will provide sufficient estimates of the effect sizes necessary to power a future two-armed randomized study

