9.6 Measures to Minimize Bias

9.6.1.1 Enrollment/Randomization/Masking Procedures

After receiving intranasal oxytocin for 9 weeks, participants will be randomized to either intranasal oxytocin or placebo. The fellow will use a random number generator to assign subjects to 0 (placebo) or 1 (active drug) each time a subject enters the randomized phase of the study. He will use block randomization so that treatment group assignments are balanced. This information will be created and stored in the Randomization Log. This will be kept securely, stored in a separate Randomization binder to ensure the non-blinded fellow only accesses the information as needed to randomize the study medication at visit 11.

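### The objective and the planned use of the effect size concern oxytocin versus placebo, but the only randomised contrast is continuing oxytocin versus switching to placebo after open-label treatment

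*Combined protocol and SAP*

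**What the plan says.** Section 3.1 gives the objective: "To significantly improve tinnitus loudness as measured by VAS, when using intranasal oxytocin compared to placebo". The hypothesis in Section 2.3 is to the same effect. Section 9.2 says of the blinded-phase result: "This effect size estimate can then be used to power future comparative studies". Section 9.5 adds: "As such the sample size of n=30 will provide sufficient estimates of the effect sizes necessary to power a future two-armed randomized study".

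The order of events is stated just as clearly. The Protocol Summary says: "The first 9 weeks of this period will involve the administration of active study medication to all participants". Section 9.6.1.1 says: "After receiving intranasal oxytocin for 9 weeks, participants will be randomized to either intranasal oxytocin or placebo". The third primary comparison in Section 3 is described openly as 15 participants on active drug for the whole study against 15 who began on active drug and were moved to placebo.

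Sections 4.2.1.1, 9.2 and 9.4.2 define the primary endpoint as the area under each participant's VAS curve from week 3 to week 6 of the blinded phase, after subtracting that participant's week-3 value. Section 9.4.2 uses the resulting partial eta squared to judge oxytocin against placebo, and counts 0.5 or more as a treatment success. Sections 9.2 and 9.4.2 treat the open-label VAS area as biased by knowledge of treatment, to be described and read with caution.

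**The concern.** No group starts on placebo, so the randomised part of the trial does not answer the question in Sections 2.3 and 3.1. It answers a different one: after a period on open-label oxytocin, what happens to those who continue compared with those who are switched? That is a legitimate question for a pilot. But in the text available, the plan neither names it as such nor explains why its effect size would carry over to a trial that starts treatment.

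Three things are at stake. A null blinded result could be read as showing that oxytocin does not improve tinnitus. A result above the success threshold could be read as superiority over placebo in untreated patients. And supplying an effect size for the next trial is the main goal stated in Section 9.5, so the number could be used to size a trial with a different comparison. This is separate from the imprecision of 15 per arm.

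**Working it through.** **What each part of the trial can estimate**

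- *Open-label phase.* Change from baseline on oxytocin, with no placebo group. Section 2.3 gives high placebo response as the reason for the run-in, but the run-in is on known active drug and cannot separate drug response from placebo response.
- *Blinded phase.* Continue versus switch, randomised 1:1 among those who reach Visit 11, with a baseline taken after randomisation.
- *Starting oxytocin versus starting placebo.* No part of the trial estimates this.

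Section 9.4.2 expects placebo VAS to stay near the week-3 value while the active arm trends. That is the pattern of a trial in which treatment starts. After open-label treatment, the switched arm may instead be the one that moves, and the plan does not discuss that case.

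**Why a null is ambiguous**

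The inputs below are my assumptions; the documents give no figure for how fast benefit is lost. Let the continuing arm hold a benefit D, and let the switched arm lose it as 1 − exp(−t/τ), with t in weeks since randomisation. With baseline at week a and follow-up to week 6, the mean between-arm difference above baseline, as a fraction of D, is

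F = exp(−a/τ) − τ[exp(−a/τ) − exp(−6/τ)]/(6 − a).

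For a = 3 and τ = 4: exp(−0.75) = 0.472 and exp(−1.5) = 0.223, so F = 0.472 − 4 × 0.249/3 = 0.140.

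The baseline may fall two or three weeks after randomisation, depending on how week 3 is counted, so both are shown.

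| τ (weeks) | F, a = 2 | F, a = 3 | Week-6 difference without re-baselining, 1 − exp(−6/τ) |
|---|---|---|---|
| 0.25 | 0.000 | 0.000 | 1.000 |
| 1 | 0.102 | 0.034 | 0.998 |
| 3 | 0.230 | 0.135 | 0.865 |
| 4 | 0.223 | 0.140 | 0.777 |
| 6 | 0.194 | 0.129 | 0.632 |
| 26 | 0.068 | 0.049 | 0.206 |

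The maximum of F is 0.230 for a = 2 (τ about 3.1) and 0.140 for a = 3 (τ about 3.9). With fast loss, the whole benefit disappears before the baseline and is subtracted out. With slow loss, the arms stay alike. Both give a contrast near zero while D is as large as one likes.

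**Why a positive result is ambiguous**

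The same area difference can come from further improvement in those who continue, from loss of benefit in those who switch, or from worsening driven by the expectation or perception of having been switched. The endpoint does not separate them.

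**Length of the open-label phase**

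The stated length is 9 weeks. By the schedule, drug is first dispensed at Visit 3, at the end of Week 1 ("Provide the study medication to the participant to use four times daily for the next 2 weeks"), and randomisation is at Visit 11, Week 9 ("Randomize and dispense new study drug (active drug or placebo nasal spray) to use for the next 2 weeks"): 9 − 1 = 8 weeks. The two must be reconciled, but that is a separate matter.

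**The case against.** The strongest reply is that the design is disclosed. Section 3 says exactly who is compared with whom, the open-label bias is acknowledged, no sentence says that a null means no benefit, and Section 9.5 does not specify the design of the future trial. All of that is true, and it makes this a mismatch of labelling and inference, not concealment. It does not remove the mismatch. The objective still claims improvement over placebo. Section 2.2 ties the later large study to a new indication, and Section 5.2 excludes prior users of the spray, both of which point towards untreated patients.

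A second reply is that Sections 2.1 and 2.4 cite a very short half-life, so benefit should be lost quickly and withdrawal should mirror treatment. The figure is a plasma half-life, not a time to return of symptoms. Even if loss is quick, the week-3 baseline removes it from the endpoint. The two excluded weeks in Section 9.4 are a real attempt to deal with carry-over, but they do not turn the contrast into one of starting treatment.

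Several stronger readings are tempting and should not be made:

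- *All improvement occurs in the uncontrolled phase.* Section 9.4.2 expects the active arm to trend under blinding. By the steps in Section 6.1.7 and the visit schedule, a participant raised at each step reaches the last one only at Week 7, two weeks before randomisation. Blinded improvement is possible.
- *The two effects would agree if all benefit were lost during the blinded phase.* Loss before week 3 is subtracted out.
- *Selection before randomisation is large.* The expected fall from 50 to 30 includes screen failures, no dropout rate is given, and randomisation is not restricted to responders.
- *A positive contrast shows maintenance of effect.* It has the other explanations given above.

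**Conclusion.** The point holds as a mismatch between the stated objective and use on one side and the randomised contrast on the other. The blinded effect size estimates continuing versus switching over the analysed window, and nothing in the plan justifies reading it as oxytocin versus placebo in untreated patients.

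The documents do not give enough to size the discrepancy. The ceilings of 14% and 23% illustrate how far the planned contrast can fall below the benefit. They rest on exponential loss, a stable continuing arm and no expectation effect; further improvement on drug or expectation-driven worsening would raise the contrast. A reader might go on to compute by how much a future trial would be wrongly sized, but that needs a true effect and an offset rate that the documents do not supply.

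The concern about future use assumes that the next trial would randomise untreated patients. The documents suggest this but do not say so. The concern about the objective does not depend on it. The change should be made before the results are interpreted.

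**What to change.** 1. In Sections 2.3, 3.1 and 9.2, reword the randomised objective: *to estimate, after the open-label phase, the effect of continuing oxytocin versus switching to placebo on VAS loudness over the analysed blinded window.*
2. In Sections 9.2 and 9.5, state that this effect size can inform only a trial of the same open-label-then-randomised design, and should not by itself size a trial that randomises untreated patients.
3. In Section 9.4.2, state that a null blinded contrast does not show absence of benefit, and that success refers to continuing versus switching, not to superiority over placebo in untreated patients.

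Reconcile the 9-week and 8-week open-label lengths separately, and do not write either into the objective.

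The cost is wording in five sections, with no change to visits, drug or sample size. The downside is a narrower claim.

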2.3 Rationale

The hypothesis is that high dose intranasal oxytocin can significantly reduce tinnitus severity and disability. We hypothesize that treatment with high dose oxytocin nasal spray will result in a significant improvement of tinnitus loudness as measured by VAS when compared to placebo.

Relatively high rates of placebo response have been seen in several studies of tinnitus. As in other subjective symptoms, such as pain and affect, short term improvement after placebo can be meaningful. Therefore, the need of run in phase to determine the true response rate to the active intervention.

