9.1 Plans (SAP)

The primary analysis is to provide an estimate of the partial eta squared effect size difference between placebo and treatment during the blinded phase of the study as well as to provide initial safety and tolerability estimates during the initial open label study phase. The effect size will be calculated and interpreted using η^2 =0.2 as a small effect, η^2 =0.5 as a medium effect, and η^2 =0.8 as a large effect (20).

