9.4.2 Analysis of the Primary Efficacy Endpoint(s)

The primary efficacy endpoint is the area under the VAS curve from baseline for all randomized participants during the blinded study phase. The week 3 data after two week washout will serve as the baseline and the interval/ratio scaled area determined using the linear trapezoidal method. The expectation is that placebo participants' post-baseline VAS data will remain relatively consistent with baseline values while active treatment will trend post-baseline. Using an LOCF imputation strategy is therefore a conservative strategy for handling missing data by understating trending in the active treatment group without introducing trending in the placebo group. The mean and standard deviation by study arm in the area under the VAS curve from baseline will be presented along with the partial eta squared effect size estimate for the mean difference between study arms. The availability of data will be determined by study arm at each post-baseline study time point during the blinded study phase to investigate the potential influence of missing data. A per-protocol analysis will also be presented to further investigate the influence of missing data on the primary efficacy endpoint.

The area under the VAS curve from baseline will similarly be determined and analyzed separately for the open label/non-blinded study phase. Since this measure is biased by participant knowledge of treatment the effect size of the mean VAS area from baseline will be determined and cautiously interpreted.

As included in Section 9.1, the effect size will be calculated and interpreted using η^2 =0.2 as a small effect, η^2 =0.5 as a medium effect, and η^2 =0.8 as a large effect (20). These cut-offs will be used to judge the strength of the treatment relative to placebo control with medium ($\eta^2 \ge 0.5$) considered a treatment "success."

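### The VAS objective claims a significant improvement over placebo, but Section 9 plans no VAS test or interval and declares success by an unsigned eta squared cut-off of 0.5, which can give a different verdict.

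*Combined protocol and SAP*

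**What the plan says.** Three places state the efficacy aim in terms of significance. The primary objective in 3.1 is "To significantly improve tinnitus loudness as measured by VAS, when using intranasal oxytocin compared to placebo". The hypothesis in 2.3 is that treatment "will result in a significant improvement of tinnitus loudness as measured by VAS when compared to placebo". The Brief Summary in the Protocol Summary also hypothesises a significant reduction, in tinnitus severity and disability.

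Section 9 takes another course. In 9.1, "The primary analysis is to provide an estimate of the partial eta squared effect size difference between placebo and treatment during the blinded phase". Section 9.2 restates the hypothesis so that treatment "will result in a large effect size as measured by partial eta squared for the difference in mean area under the curve". Sections 9.1 and 9.4.2 set eta squared of 0.2, 0.5 and 0.8 as small, medium and large. Section 9.4.2 adds a pass mark: "These cut-offs will be used to judge the strength of the treatment relative to placebo control with medium" (at least 0.5) counted as a treatment success.

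For VAS, sections 9.1 to 9.4.2 list means, standard deviations and partial eta squared. They name no test, alpha, sidedness or confidence interval. The one p threshold in the documents, p < 0.10, is attached to THI/CGI and TFI (Protocol Summary and 4.1). Section 9.5 gives n = 30 with estimation as the main goal, and no alpha, power, SD or expected difference.

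Other VAS criteria stand alongside these. Section 4.1 names an improvement of more than 50% as the primary outcome measure, and Section 3 lists three VAS comparisons as primary.

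**The concern.** The objective asks whether oxytocin is significantly better than placebo on VAS, and the analysis section gives no means of answering. It supplies a different yes/no rule, and no passage says how the two relate. An observed effect could therefore meet the objective as worded and still fail the 9.4.2 rule, so the reported verdict would depend on which section is cited.

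Two features make this more than loose wording. First, with alpha and sidedness unstated, the significance standard can be settled after the data are seen; 9.4 also leaves the analyses open to refinement up to data lock. Second, eta squared carries no sign, so the 9.4.2 rule as written would label a large difference in favour of placebo a success.

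**Working it through.** **Inputs.** n = 30 (9.5), with half on each arm in the blinded phase (4.1), so 15 per arm, as Section 3 also says. Success cut-off 0.5 (9.4.2); large effect 0.8 (9.1). Assumed, because the documents are silent: a two-arm comparison of VAS area with no covariate (partial eta squared then equals eta squared), normal outcome, equal variances, two-sided alpha 0.05, and the true standardised difference d.

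**Plan's own figure.** n = 30 cannot be reproduced, and no alpha can be back-solved from it, because 9.5 gives no inputs.

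**Common scale.** With 28 degrees of freedom:

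- eta squared = t² / (t² + 28), so t² = 28 × eta squared / (1 − eta squared)
- d = t × √(2/15)

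| Point on the scale | t | eta squared | observed d | two-sided p |
|---|---|---|---|---|
| two-sided 0.10 | 1.701 | 0.094 | 0.62 | 0.10 |
| two-sided 0.05 | 2.048 | 0.130 | 0.75 | 0.05 |
| example | √12 = 3.464 | 0.30 | 1.26 | 0.0017 |
| success rule | √28 = 5.292 | 0.50 | 1.93 | 0.0000125 |
| plan's large effect | √112 = 10.583 | 0.80 | 3.86 | 2.7 × 10⁻¹¹ |

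For the second row: 2.048² = 4.196, and 4.196 / 32.196 = 0.130. Every favourable result from 0.130 to just under 0.5 is significant at the assumed level but is not a success. The example row is one such result.

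**How often the verdicts differ.** For true d, t follows a noncentral t distribution with noncentrality d × √7.5. The chance of significance without success is P(t > 2.048) − P(t > 5.292). The last column covers the case in which the 0.5 cut-off was meant as a standardised mean difference. An observed d of 0.5 gives t = 0.5 × √7.5 = 1.369 and p about 0.18, so the mismatch becomes success without significance, P(1.369 < t < 2.048).

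| True d (assumed) | favourable p < 0.05 | eta squared ≥ 0.5 | significant, not success | if cut-off is d: success, not significant |
|---|---|---|---|---|
| 0.5 | 26.2% | 0.07% | 26% | 24% |
| 0.8 | 56.2% | 0.6% | 56% | 23% |
| 1.2 | 88.7% | 5.4% | 83% | 8% |
| 1.5 | 97.7% | 17.7% | 80% | 2% |
| 2.0 | 99.96% | 57.7% | 42% | under 0.1% |
| 3.86 | about 100% | 99.999% | about 0.001% | negligible |

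Simulation of 200,000 trials at each of d = 0.8, 1.2 and 2.0 agreed with the two probability columns (for example 56.1% and 0.6% at d = 0.8).

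**Sensitivity.** At two-sided 0.10 the chance of significance without success is 68% at d = 0.8 and 81% at d = 1.5. With 10 per arm the band of disagreement is still eta squared 0.197 to 0.5.

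**The case against.** The strongest reply is that only one decision rule exists. Sections 2.3 and 3.1 name no statistic or alpha, and elsewhere the documents use the word significant in an everyday sense, for instance for a rise in blood pressure in 5.7. Section 9.2 appears to replace the significance hypothesis with an effect-size one, and 9.1 and 9.5 say that the aim is estimation. A pilot needs no hypothesis test. On this view what remains is wording left unharmonised.

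Much of that stands. The absence of a test is not itself the defect, and the 5% level used above is an assumption. It is also an assumption that 3.1 refers to the VAS area in 9.4.2, since 3.1 names only VAS loudness. What the reply does not answer is that 3.1 is the formal primary objective, that nothing withdraws its wording, and that 9.4.2 goes beyond estimation by adding a pass/fail rule of its own.

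A reader might infer that the two standards contradict each other. They do not: at 15 per arm any favourable eta squared of 0.5 or more is also significant at the usual levels, and a result that is significant but below a higher bar is coherent. A reader might also infer that most plausible positive results would fall into the gap. The documents give no SD or expected VAS difference, so they cannot say which effects are plausible, and at the plan's own hypothesised effect the gap almost vanishes. Finally, nothing in the text applies the p < 0.10 level to VAS or mentions a one-sided test.

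**Conclusion.** The point holds in a limited form. The objective is worded as a significance claim that Section 9 neither implements nor withdraws, while 9.4.2 sets an unsigned point-estimate rule for success. On the literal eta squared scale, an observed value of 0.30 (p = 0.0017) would meet the objective as worded at the assumed level and not count as a success, and a large harm would count as one.

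The size and direction of the mismatch rest on assumptions. Read literally, its chance lies between 26% and 83% for the assumed true d of 0.5 to 2.0, and is about 0.001% at d = 3.86. Read on the d scale it runs the other way, from 24% at d = 0.5 to under 0.1% at d = 2.0. Correcting the cut-off labels alone would change the mismatch without removing it. Data collection and safety are not affected. What is affected is how the primary result is declared.

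**What to change.** Since 9.1 and 9.5 make estimation the aim, carry it through:

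- In 2.3, 3.1, the Protocol Summary hypothesis and the large-effect hypothesis in 9.2, reword to: *to estimate the difference in blinded-phase VAS area between oxytocin and placebo*.
- In 9.4.2, replace the success sentence with the signed between-arm mean difference in VAS area and its two-sided 95% confidence interval. Keep eta squared as a descriptive figure, and state that no efficacy claim rests on a cut-off.
- State that this contrast is the single primary one. Make the improvement of more than 50% in 4.1 and the three VAS comparisons in Section 3 secondary or descriptive.

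The cost is edits to those sections and one extra line of output, with no new patients or data. The sponsor gives up the word significantly and the success label.
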